#### Model

For each treatment separately, Bayesian methodology will be used to fit the following nonlinear mixed effects model to the observed pre-BD FEV1 change from baseline data

$$y_{ij} = C_i(1 - e^{-\theta_i^* t_{ij}}) + \varepsilon_{ij}$$

where  $y_{ij}$  denotes the change from baseline value for the  $i$ -th subject at the  $j$ -th time point ( $i = 1, \dots, n; j = 1, \dots, 7$ )

$$\varepsilon_{ij} \sim t(0, \sigma^2, df)$$

$$C_i \sim N(C, \sigma_C^2)$$

$$\theta_i^* = e^{1 + \varepsilon \theta_i}$$

$$\log \theta_i \sim N(\log \theta, \sigma_{\log \theta}^2)$$

Note that  $C$  is an asymptote, representing the maximum (or minimum) change from baseline over time and  $\theta$  is a rate, constrained to be greater than zero, representing how quickly the change from baseline values increase or decrease over time. This model takes into account the inherent structure that is present in the observed data and gives an estimate of  $C$  and  $\theta$  for a specific treatment group, and allows these parameters to vary between subjects.

Prior distributions for the model parameters will be:

$$C \sim N(0, 1e6)$$

$$\log \theta \sim N(0, 1e6)$$

$$\sigma^2 \sim \text{igamma}(\text{shape}=0.01, \text{scale}=0.01)$$

$$\sigma_C^2 \sim \text{igamma}(\text{shape}=0.01, \text{scale}=0.01)$$

$$\sigma_{\log \theta}^2 \sim \text{igamma}(\text{shape}=0.01, \text{scale}=0.01)$$

$$df \sim \text{uniform}(2, 50)$$

Note that igamma refers to inverse gamma distribution.

For each parameter, a chain of 200,000 samples will be drawn from the posterior distribution, after discarding the first 100,000 burn-in samples. The 200,000 samples will be thinned every 200th observation to ensure there is little correlation in the remaining 1,000 posterior samples. Following the same process, a further two chains will be run, whereby the seed and set of starting values will be changed for each of these additional chains. Seed numbers of 3598, 2917 and 6301 will be utilized for benralizumab, and seed numbers of 1256, 8734 and 7376 for placebo group. Starting values for both treatment groups will be 25, 50 and 75 mL for  $C$ , and -1 for  $\log \theta$ . Sensitivity analysis may be carried out for different starting values from those specified to assess the robustness of model fitting.

Note that when modelling the pre-BD FEV1 measurements, data collected beyond Day 98 (upper visit window of Day 84) will be excluded in the analysis.

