## 1.3 Number of subjects

The study will recruit approximately 230 patients in total and 115 patients in each treatment group based on the primary objective of the study to determine the effect of benralizumab on the time course of change (onset and maintenance of effect) of pre-bronchodilator (BD) FEV1.

Patients will be randomized in a 1:1 ratio to benralizumab or placebo. In order to have a balanced number of patients for each region and the body plethysmography sub-study, the randomization will be stratified by these variables.

The study is powered for the primary objective of the study to determine the effect of benralizumab on the time course of change (onset and maintenance of effect) of pre-BD FEV1.

The first post-baseline timepoint where the p-value for the mean difference between benralizumab and placebo is  $\leq 0.05$  will be used to determine time to onset of effect. The average over the mean differences between benralizumab and placebo based on the change from baseline (Visit 4) to Days 28 (Visit 8), 56 (Visit 9), and 84 (Visit 10) in pre-BD FEV1 will be used to determine if the study is positive and to determine maintenance of effect.

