The results of the Phase 2b study, MI-CP220 (Castro et al 2014) and the Phase 3 asthma exacerbation studies, SIROCCO (Bleeker et al 2016) and CALIMA (Fitzgerald et al 2016) were used as a basis for the sample sizing. From these studies, it is expected that around 115 patients per treatment arm (230 in total) will provide approximately 90% power for the primary endpoint pre-BD FEV1 with type I error controlled at a two-sided alpha level of 0.05 if the true average over the mean treatment differences (benralizumab – placebo) across Days 28 (Visit 8), 56 (Visit 9), and 84 (Visit 10) is 138 mL. The sample size will also be sufficient to have approximately 80% power for an average over the mean treatment difference of 120 mL. The assumed variability has a within-group standard deviation of 375 mL and within-patient correlation of 0.6. If the within-patient variability is reduced to 350 mL, the sample size would be sufficient 80% power for an average of 110 mL. In addition, it is expected that around 115 patients per treatment arm will have 80% power to detect a true treatment difference (benralizumab – placebo) of 130 mL, assuming a within-group standard deviation of 350 mL or a true treatment difference of 140 mL, assuming a standard deviation of 375 mL. Based on these assumptions, the minimum difference that would be statistically significant at the 5% level ranges from approximately 85 to 100 mL. The sample size was estimated using nQuery + nTerim version 3.0 using methodology by Liu et al (Liu et al 2005).

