#### **4.2.5 Primary outcome variable**

##### **4.2.5.1 Primary analysis**

The change from baseline in pre-BD FEV1 up until the EOT at Visit 10 will be compared between the 30 mg benralizumab group and placebo using a mixed-effect model for repeated measures (MMRM) analysis on patients with a baseline pre-BD FEV1 and at least 1 post-randomization pre-BD FEV1 in the FAS.

The dependent variable will be the change from baseline in pre-BD FEV1 at post-baseline protocol specific visits (up to and including the EOT Visit). Treatment group will be fitted as the explanatory variable, region, visit and treatment\*visit interaction as fixed effects, and baseline pre-BD FEV1 will be fitted as a covariate. The variance-covariance matrix will be assumed to be unstructured. If the procedure does not converge, then a compound symmetric variance-covariance matrix will be used instead. The model is:

$$\text{Change in FEV}_1 = \text{treatment} + \text{baseline pre-BD FEV}_1 + \text{region} + \text{visit} + \text{treatment} * \text{visit}$$

The primary objective of the study is to determine the effect of benralizumab on the time course of change (onset and maintenance of effect) of pre-BD FEV1 using the model described above. The first post-baseline timepoint where the p-value for the mean difference between benralizumab and placebo is  $\leq 0.05$  will be used to determine time to onset of effect. The average over the mean differences between benralizumab and placebo based on the change from baseline (Visit 4) to Days 28 (Visit 8), 56 (Visit 9), and 84 (Visit 10) in pre-BD FEV1 will be used to determine if the study is positive as well as to determine the

maintenance of effect. Contrasts will be used to obtain estimates of the treatment differences over Days 28, 56, and 84, as well as at each timepoint separately.

Results will be presented in terms of least square means (LSMEANS), treatment differences in LSMEANS, 95% confidence intervals (CI) of treatment differences, and p-values at each planned timepoint.

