- v. The difference between treatment groups in mean change from baseline value at time  $t$  for the  $k$ -th posterior sample will be calculated as (mean change from baseline value in benralizumab) – (mean change from baseline value in placebo), where mean within treatment group is derived as per step ii above.
- vi. The 50th and (2.5th, 97.5th) percentiles of the differences  $\{d_1, \dots, d_{3000}\}$  at time  $t$  will be derived, giving the median and corresponding 95% credible interval for the difference between benralizumab and placebo in change from baseline at time  $t$ . If either the 50th, 2.5th or 97.5th percentile is greater than  $T=84$ , such values will be reported as “>84”.

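### The supportive onset model leaves out baseline FEV1, so chance baseline imbalance stays in the modelled difference and time to threshold

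*SAP*

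**What the plan says.** In the primary repeated-measures model (SAP 4.2.5.1; Protocol 8.5.1), region is a fixed effect and baseline pre-BD FEV1 "will be fitted as a covariate". Two other FEV1 comparisons also keep baseline: the simplified ANCOVA for the standardised effects plot (SAP 4.2.5.3), which drops region, and the FEV1 responder model (SAP 4.2.6.1).

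The onset model in SAP 4.2.5.4 differs: "For each treatment separately, Bayesian methodology will be used to fit the following nonlinear mixed effects model to the observed" changes from baseline. Each patient's curve is C_i(1 − exp(−θ_i* t)) plus error, with C_i and log θ_i scattered around one mean per arm. There is no baseline or region term. The arm curve is the plain average of the patients' fitted curves. "The difference between treatment groups in mean change from baseline value at time" t is then the benralizumab average minus the placebo average, and times to the 50 to 300 mL differences are read from the same curves. No later step brings the arms to a common baseline. The fallback options change priors, distributions or curve shape and add no covariate.

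Randomisation is stratified by region and sub-study participation only (Protocol 3.6; SAP 1.3). SAP 4.2.5.4 restricts the onset analysis to patients who have a baseline value.

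**The concern.** Change from baseline usually falls as baseline rises, partly through regression to the mean. An arm that starts lower by chance will then tend to gain more, whatever its treatment. The adjusted models remove this component and the onset model does not. The modelled difference can therefore depart from the primary model's difference because of baseline imbalance alone, and a reader could not separate that from the effect of the curve shape. Time to a threshold is the most exposed output, because it changes steeply when the threshold lies near the plateau difference. Onset is the study's stated question, and this model supplies onset times between visits with credible intervals, so the gap deserves closing even though the analysis is supportive.

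**Working it through.** **1. The plan's own figure.** SAP 1.3 states that "around 115 patients per treatment arm (230 in total) will provide approximately 90% power", with "type I error controlled at a two-sided alpha level of 0.05", for a true Day 28/56/84 average of 138 mL and a "within-group standard deviation of 375 mL and within-patient correlation of 0.6".
- SD of the three-visit average = 375 × √((1 + 2 × 0.6)/3) = 321.1 mL
- SE of the difference = 321.1 × √(2/115) = 42.35 mL
- Power = Φ(138/42.35 − 1.96) = Φ(1.30) = 90.3%, so the stated figure is reproduced.

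**2. Shift from chance imbalance.** The documents give no baseline SD. Assume SDb between 550 and 750 mL and equal variance at baseline and follow-up. Then 375² = 2 SDb²(1 − r), and the slope of change on baseline is b = −(1 − r) = −375²/(2 SDb²). The SE of the imbalance is SDb √(2/115). The share of variance explained is (b SDb)²/321.1², and the fall in SE is 1 − √(1 − share).

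| SDb (mL) | b | SE of imbalance (mL) | Shift at 1 SE (mL) | Shift at 2 SE (mL) | Variance share | Fall in SE |
|---|---|---|---|---|---|---|
| 550 | −0.232 | 72.5 | 16.9 | 33.7 | 15.8% | 8.3% |
| 750 | −0.125 | 98.9 | 12.4 | 24.7 | 8.5% | 4.4% |

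Against 138 mL, the shift is 9 to 12% at 1 SE and 18 to 24% at 2 SE. With wider assumptions (SDb 500 to 800 mL, slope −0.05 to −0.3), the 1-SE shift runs from 3 to 32 mL. At slope −0.05 it is only 3 to 5 mL.

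**3. Time to a 100 mL difference.** Assume a plateau difference P = 138 mL and a 14-day half-time, and treat the shift as a change in P. Then t = −ln(1 − 100/P) × 14/ln 2 = 26 days. Using the larger shifts from the table:
- P = 138 ± 16.9 gives 21 and 35 days.
- P = 138 ± 33.7 gives 18 and 64 days.

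**4. Mechanism by simulation.** There were 2,000 trials per scenario with baseline SD 700 mL, plateau difference 138 mL and rate 0.1 per day. An exponential was fitted to each arm's mean profile by least squares, as an approximation to the Bayesian model.
- For true slopes −0.1, −0.2 and −0.3, the modelled Day 28/56/84 difference moved with imbalance at −0.10, −0.19 and −0.29. ANCOVA moved at about zero.
- Median time to 100 mL was about 12 days overall. At slope −0.2 it was 7 days when the benralizumab baseline was more than 1 SE below placebo, and 26 days when it was more than 1 SE above.
- At slope 0 nothing moved (12.0 against 12.3 days).
- Mean unadjusted and adjusted estimates agreed (134.3 and 134.1 mL at slope −0.2), so there is no systematic bias.

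**5. Form of the adjustment.** This was a least-squares simulation with a slope constant over time, a 14-day half-time and a true time to 100 mL of 26 days.

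| Model | Median time to 100 mL (days) |
|---|---|
| No baseline term | 27 |
| Baseline on C_i | 19 |
| Baseline term constant over time | 26.5 |

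Baseline on C_i also raised the SD of the Day 84 difference. The constant term lowered the SD and left almost no dependence on imbalance. The reason is that regression to the mean is present in full at the first post-baseline visit. Tying it to 1 − exp(−θt) makes it grow at the treatment curve's rate and distorts that rate. In a similar simulation with a 5-day half-time the distortion was small (8.9 days unadjusted, 7.8 with baseline on C_i).

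**The case against.** The strongest reply is that little depends on this model. The study-positive contrast, maintenance of effect and the p-value rule for onset all come from the adjusted repeated-measures model, and SAP 4.1 makes every other p-value nominal. Adjusted counterparts exist for two of the outputs: the first visit at which the repeated-measures difference exceeds given thresholds (Protocol 8.5.1), and responders at the same 50 to 300 mL cut-offs (SAP 3.2.1 and 4.2.6.1). That stands. What remains unadjusted is the interpolated curve and the times read from it.

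The reply can add that the time-to-threshold example mostly reflects how close 100 mL lies to an assumed 138 mL plateau. Ordinary 1-SE sampling error (138 ± 42.35 mL) already moves the time from 16 days to never reached, because 95.65 mL is below 100. That also stands: adjustment removes one avoidable part of the uncertainty, not most of it.

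Several design features limit regression to the mean. Two Day 0 readings are averaged (SAP 2.2.3), patients whose Day 0 value changed by 20% or more are excluded (Protocol 3.3.2), and the under-80% criterion is applied at Visits 2 or 3 rather than at baseline (Protocol 3.1). These may bring the slope towards zero, but they do not show that it is zero.

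Protocol 8.5.1 also names no covariates for the exponential model, so the two documents do not contradict each other here. The inconsistency is with the SAP's own handling of FEV1 elsewhere.

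**Conclusion.** The point holds as an avoidable gap in a supportive analysis. The onset model omits a covariate that the SAP's other FEV1 comparisons keep and that every modelled patient has. With a baseline SD of 550 to 750 mL and equal variances, the cost is 8 to 16% of the variance of the Day 28/56/84 average (4 to 8% of its SE), and a typical conditional shift is 12 to 17 mL. The shift in time to threshold depends further on the assumed plateau and half-time. If the slope is near zero, the effect is negligible.

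A reader might infer three stronger things that the documents do not support:
- **That modelled onset is biased.** Under 1:1 randomisation the imbalance averages to zero. It also enters multiplied by the slope, not one-for-one, because change scores already subtract baseline.
- **That the trial's main conclusion is at risk.** That conclusion comes from the adjusted model.
- **That omitting region matters equally.** Region is a stratification factor, so chance imbalance by region should be small. Baseline FEV1 is the substantive omission.

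**What to change.** In SAP 4.2.5.4, add a centred baseline term that is constant over time:

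y_ij = β(baseline_i − pooled mean over both arms) + C_i(1 − exp(−θ_i* t_ij)) + error.

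Compute the arm curves, the differences and the times to threshold at the pooled baseline mean, where the β term is zero. The arms can still be fitted separately, each with its own β. Make this the main onset model, or at least a pre-specified sensitivity analysis reported beside the current one. Do not put baseline on C_i alone. A region term is optional. The modelled responder proportions and odds ratios come from the same fits, so the SAP should also say how baseline is handled there.

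The cost is SAP wording, one more parameter per arm, and a little more model checking, including whether a slope constant over time fits the data. It needs no new data and no more patients.

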## Model checks

The convergence of the model will be investigated by assessing stationarity and mixing across chains. If convergence is not met, it may be deemed necessary to consider alternatives for (i) the set of priors, (ii) the distributions associated with the model parameters describing the data, (iii) the exponential model. Any deviation from the planned analysis will be documented as a change to the statistical analysis plan.

- Stationarity

For each parameter, the 1000 posterior samples will be plotted against iteration number for each chain separately. Posterior summary will be provided for C and  $\log \theta$  from each chain, the efficiency associated with the effective sample size will also be checked for each parameter to ensure that this statistic is high (e.g. greater than 0.9) across chains. If an obvious pattern exists in the posterior samples or the efficiency  $< 0.9$  for a specific chain, auto-correlation exists and stationarity has not been reached. Consequently, a larger number of samples will be discarded as burn-in, and the number of samples per chain will be increased with a greater amount of thinning.

- Mixing

For each parameter, the 1000 posterior samples from each chain will be plotted together against iteration number, with a different coloured line used for each chain. If the chains overlap, they are deemed to mix well and they will be combined to give 3000 posterior samples for each model parameter. If the chains do not mix well, the proposed model will be reviewed and refined if deemed necessary.

### Estimating the change from baseline at time points of interest in a treatment group, and difference in change from baseline at time points of interest between treatment groups

For a specific treatment group, let  $\{C_{ik}, \log \theta_{ik}\}$  denote the set of estimated model parameters for the  $i$ -th subject from the  $k$ -th posterior sample, where  $i = 1, \dots, n$  and  $k = 1, \dots, 3000$  (assuming the 3 chains are stationary and mix well). Let  $t$  denote a time point of interest, where  $t=1, 3, 7, 14, 21, 28, 58, 84$ . The change from baseline at each time point of interest will be estimated for benralizumab and placebo by following the steps below:

- For the  $k$ -th posterior sample ( $k = 1, \dots, 3000$ ), the fitted change from baseline value at time point  $t$  for the  $i$ -th subject ( $i = 1, \dots, n$ ) in a specific treatment group is

$$y_{ik}(t) = C_{ik}(1 - e^{-\theta_{ik}^* t})$$

$$\text{where } \theta_{ik}^* = e^{\log \theta_{ik}}.$$

- The mean change from baseline value at time  $t$  for the  $k$ -th posterior sample will be calculated as

$$\bar{y}_k(t) = \frac{1}{n} \sum_{i=1}^n y_{ik}(t)$$

- iii. The 50th and (2.5th, 97.5th) percentiles of  $\{\bar{y}_1(t), \dots, \bar{y}_{3000}(t)\}$  will be derived, giving the median and corresponding 95% credible interval for the average change from baseline value at time point  $t$
- iv. Steps (i) through to (iii) will be carried out for each treatment and all values of  $t$ .

Note that it is anticipated that some subjects may withdraw from the study early. For these subjects, their fitted response will be extrapolated beyond their last visit. Consequently, inferences will be based on all subjects in the analysis set.

Estimates and credible intervals for the change from baseline from the modelling above will be tabulated by treatment and time point. A figure will be provided for the change from baseline values over time.

To estimate the difference between treatment groups in change from baseline at time points of interest, assuming the 3 chains are stationary and mix well, by independence the  $k$ -th posterior sample for benralizumab will be associated with the  $k$ -th posterior sample for placebo ( $k = 1, \dots, 3000$ ).

- v. The difference between treatment groups in mean change from baseline value at time  $t$  for the  $k$ -th posterior sample will be calculated as (mean change from baseline value in benralizumab) – (mean change from baseline value in placebo), where mean within treatment group is derived as per step ii above.
- vi. The 50th and (2.5th, 97.5th) percentiles of the differences  $\{d_1, \dots, d_{3000}\}$  at time  $t$  will be derived, giving the median and corresponding 95% credible interval for the difference between benralizumab and placebo in change from baseline at time  $t$ . If either the 50th, 2.5th or 97.5th percentile is greater than  $T=84$ , such values will be reported as “>84”.

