#### 4.2.5.4 Supportive analyses

The modelled treatment response as well as differences between benralizumab and placebo using the mean change from baseline in pre-BD FEV1 endpoint using an exponential model over time will be estimated. The model will be used to determine the modelled time to onset of effect.

Onset of effect will be defined as: (i) the time taken for benralizumab and placebo to reach a pre-defined change from baseline value, (ii) the time taken for the difference between benralizumab and placebo [change from baseline values to reach a pre-defined value.

As detailed in the study protocol, the main focus is to estimate onset of effect using the primary variable, pre-BD FEV1. Onset of effect will be estimated using change from baseline measurements which were scheduled on days 3, 7, 14, 28, 56, and 84, actual day that data is collected in study is utilized. An exponential relationship will be assumed over time ([Gelman, et al 2013](#)), using Bayesian methodology ([Marostica, et al 2013](#)) to fit a nonlinear mixed effects model to the observed data. The fitted model will then be used to estimate onset of effect for the set of change from baseline values 50, 100, 150, 200, 250, and 300 mL and the set of differences 50, 100, 150, 200, 250, and 300 mL. In addition, an average change from baseline will be estimated for days 1, 3, 7, 14, 21 and 28, 56, 84, and the proportion of subjects with a change from baseline value greater than or equal to {50, 100, 150, 200 and 250 and 300 mL} will be estimated for days 1, 3, 7, 14, 21, 28, 56, 84. Differences between proportions and odds ratios will also be estimated.

It is anticipated that an exponential model will adequately describe pre-BD FEV1 change from baseline over time, based on ([Gelman, et al 2013](#)) and modelling similar data taken from the Phase III SIROCCO and CALIMA trials. However, if the data show that an exponential model is a poor choice, an alternative model will be investigated following the same principles outlined below.

In addition to pre-BD FEV1, one or more secondary variables may also be investigated.

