### Estimating the time taken for a treatment to reach a pre-defined change from baseline value

For a specific treatment group, let  $\{C_{ik}, \log \theta_{ik}\}$  denote the set of estimated model parameters for the  $i$ -th subject from the  $k$ -th posterior sample, where  $i = 1, \dots, n$  and  $k = 1, \dots, 3000$  (assuming the 3 chains are stationary and mix well). Let  $\Delta$  denote a pre-defined change from baseline value, where  $\Delta = 50, 100, 150, 200, 250, \text{ and } 300$  mL. Let  $T$  be the *planned* duration of the study in days, where  $T=84$  is divided into 1000 time points to give  $\{t_1, \dots, t_{1000}\}$ . The time taken to reach a pre-defined change from baseline value will be estimated for benralizumab and placebo by following the steps below:

- i. For the  $k$ -th posterior sample ( $k = 1, \dots, 3000$ ), the fitted change from baseline at time point  $t_j$  ( $j = 1, \dots, 1000$ ) for the  $i$ -th subject ( $i = 1, \dots, n$ ) in a specific treatment group is

$$y_{ik}(t) = C_{ik}(1 - e^{-\theta_{ik}^* t})$$

where  $\theta_{ik}^* = e^{\log \theta_{ik}}$ .

- ii. The mean change from baseline value at time  $t_j$  for the  $k$ -th posterior sample will be calculated as

$$\bar{y}_k(t_j) = \frac{1}{n} \sum_{i=1}^n y_{ik}(t_j)$$

- iii. For pre-BD FEV1, an improvement is associated with  $\Delta > 0$ . Thus, from the set of values  $\{\bar{y}_k(t_1), \dots, \bar{y}_k(t_{1000})\}$ , all values greater than or equal to a specific value of  $\Delta$  will be retained. The earliest time point will be selected and labelled  $t_k^*$  (which gives the earliest time point at which  $\bar{y}_k(t_j)$  is closest to  $\Delta$ ). If there are no values that are greater than or equal to  $\Delta$ , the time  $t_k^*$  will be set to a large value greater than  $T$  (e.g.  $t_k^* = 10000$ ). Consequently, all posterior samples will be included in the summary of  $\{t_1^*, \dots, t_{3000}^*\}$ .
- iv. The 50th and (2.5th, 97.5th) percentiles of  $\{t_1^*, \dots, t_{3000}^*\}$  will be derived, giving the median and corresponding 95% credible interval for the average time taken for the change from baseline to reach  $\Delta$ . If either the 50th, 2.5th or 97.5th percentile is greater than  $T=84$ , such values will be reported as “>84”.
- v. Steps (i) through to (iv) will be carried out for each treatment and all values of  $\Delta$

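### The SAP applies a reporting cut-off of 84 days to treatment differences in mL, so modelled differences of the planned size would print as `>84` instead of their value

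*SAP*

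**What the plan says.** SAP 4.2.5.4 (Supportive analyses) fits an exponential model to change from baseline in pre-BD FEV1 and derives several outputs from its posterior samples.

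- **Difference at a fixed time.** Step v of the sub-section on change from baseline at time points of interest defines, for each posterior sample, the benralizumab mean change minus the placebo mean change at time t. Step vi takes the 50th, 2.5th and 97.5th percentiles, "giving the median and corresponding 95% credible interval for the difference between benralizumab and placebo in change from baseline at time" t. Its next sentence says that if any of these is greater than T=84, "such values will be reported as" `>84`.
- **Meaning of T.** T is defined only in the following sub-section, on time to reach a pre-defined change, where it is said to "be the *planned* duration of the study in days".
- **Where the same rule fits.** Step iv of that sub-section applies it to times, "giving the median and corresponding 95% credible interval for the average time taken for the change from baseline to reach" the threshold. Step v of the sub-section on time for the difference to reach a threshold does the same. Both work in days.
- **Time grid.** The grid for the fixed-time outputs is "t=1, 3, 7, 14, 21, 28, 58, 84", and the sub-section on responder proportions repeats it. The opening of 4.2.5.4 says "an average change from baseline will be estimated for days 1, 3, 7, 14, 21 and 28, 56, 84", and the fallback under Alternative models also uses 56.

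**The concern.** A volume is being compared with a number of days. The model runs in mL: the starting values for the asymptote are 25, 50 and 75 mL, and every threshold lies between 50 and 300 mL. A cut at 84 has no meaning on that scale.

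The sentence appears to have been carried over from the time-to-threshold steps. There, posterior samples that never reach the threshold are given an arbitrary large time such as 10000, so a cap at the end of the study is needed. A difference at a fixed time has no such censoring. The matching within-group summary (step iii of the same sub-section) has no cap, so arm means above 84 mL would print in full while their difference would not.

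Protocol 8.5.1 names the modelled differences between benralizumab and placebo among the analyses supporting the primary objective. Programmed literally, the table loses its point estimate and upper limit when the drug performs as planned. If a programmer quietly corrects the rule, the output departs from the SAP, which asks for deviations from the planned analysis to be documented.

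The Day 58 entries are a separate slip: the SAP contradicts itself about which time point is to be tabulated.

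**Working it through.** **Inputs** (SAP 1.3): 115 patients per arm; within-group SD 375 mL (alternative 350 mL); within-patient correlation 0.6; two-sided alpha 0.05; average differences over Days 28, 56 and 84 of 138, 120 and 110 mL; single differences of 130 and 140 mL.

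**1. The plan's own power figures.** For the average of three visits, effective SD = SD × √((1 + 2 × 0.6)/3), which is 321.1 mL (SD 375) or 299.7 mL (SD 350). SE = effective SD × √(2/115) = 42.3 or 39.5 mL. Power = Φ(difference/SE − 1.96).

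| Difference | SD | Stated power | Recomputed |
|---|---|---|---|
| 138 mL, average | 375 | about 90% | 90.3% |
| 120 mL, average | 375 | about 80% | 80.9% |
| 110 mL, average | 350 | 80% | 79.5% |
| 130 mL, single | 350 | 80% | 80.4% |
| 140 mL, single | 375 | 80% | 80.8% |

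The last two rows use SE = SD × √(2/115). The stated figures reproduce, so these SDs and sample size are a sound basis for the next steps.

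**2. What the rule does to a planned result.** Take difference ± 1.96 × SE with the averaged SE.

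| Difference (95% interval), mL | As step vi would print it |
|---|---|
| 138 (55.0 to 221.0) | >84 (55.0 to >84) |
| 120 (37.0 to 203.0) | >84 (37.0 to >84) |
| 110 (32.5 to 187.5) | >84 (32.5 to >84) |

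**3. How often masking occurs at a single time point.** SE = SD × √(2/115) = 46.2 mL (SD 350) or 49.5 mL (SD 375). With true difference d and a posterior close to normal around the estimate:

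- P(median masked) = 1 − Φ((84 − d)/SE)
- P(upper limit masked) = 1 − Φ((84 − 1.96 × SE − d)/SE)

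| True d (mL) | Median masked | Upper limit masked |
|---|---|---|
| 50 | 23–25% | 89–90% |
| 110 | 70–71% | 99.4% |
| 120 | 77–78% | 99.6–99.7% |
| 138 | 86–88% | 99.9% |

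The upper limit passes 84 once the estimate exceeds 84 − 1.96 × SE, which is −6.5 mL (SD 350) or −12.9 mL (SD 375). At single-visit precision, an estimate of zero would therefore still have its upper limit masked.

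**4. Day 58 against Day 56.** For a curve C(1 − e^(−θt)), moving from 56 to 58 changes the value by C(e^(−56θ) − e^(−58θ)). This is largest at θ = ln(58/56)/2 = 0.0175, where it is 0.0129 × C, or 1.8 mL for C = 138 mL.

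**The case against.** The strongest reply is that this is a reporting slip in a supportive table. It changes no model, posterior sample, test or decision rule. SAP 4.2.5.4 puts its main focus on time to onset, and those outputs carry the cap correctly. The primary analysis (SAP 4.2.5.1) still gives differences with 95% confidence intervals at every planned time point. The modelled arm means are tabulated without a cap, so a reader could approximate the modelled median difference, though not its interval. Lower limits would usually still print, and a programmer might well query the rule.

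The percentages are also illustrative. The 110, 120 and 138 mL effects are three-visit averages, whereas step vi reports single days, including early ones where differences may be smaller. A model pooling visits may be more precise than the single-visit SE.

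All of this limits the importance, and none of it makes the rule correct. Greater precision would make masking of the median more likely for any true difference above 84 mL. SAP 2.2.2 labels pre-BD FEV1 in litres; on that scale the rule would never trigger, but it would be just as meaningless, and this model is specified in mL.

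On Day 58 the reply largely succeeds as to consequence. Day 58 lies inside the Visit 9 window, and the grid already includes Days 1 and 21, which are not scheduled visits. What remains is an inconsistency to correct.

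**Conclusion.** The concern holds. Step vi is wrong as written: it censors a difference in mL at a study length in days, and nothing elsewhere in the SAP corrects it. At the planned effects of 110 to 138 mL, the median would be masked in roughly 70–88% of trials and the upper limit in more than 99%. These figures assume a near-normal posterior, a vague prior, the plan's SDs and the single-visit SE, and they use the planned averages as a guide to size at single days. The simpler point needs none of those assumptions: every effect in the power section is above 84.

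The damage is confined to the modelled-difference output. The primary analysis, the power and the criterion for a positive study are untouched. The Day 58 entries are an error of under 2 mL for an asymptote of 138 mL and add nothing to the seriousness. The correction should be made because the error is definite and sits in a pre-specified output supporting the primary objective.

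**What to change.** Make three small edits in SAP 4.2.5.4:

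1. Delete the `>84` sentence from step vi of the sub-section on change from baseline at time points of interest, so that the median and credible limits of the difference are reported in mL as estimated. Keep the sentence in the two time-to-threshold sub-sections.
2. Change 58 to 56 in the time grid of that same sub-section.
3. Change 58 to 56 in the time grid of the sub-section on the proportion of subjects at or above pre-defined thresholds.

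The cost is the text edits alone, with no change to data collection, model fitting or analysis time.
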